12. CORRELATIVE/SPECIAL STUDIES

12.1 Plasma Inhibitory Assay

Sampling Strategy

Samples collected during study of crenolanib therapy will be collected into heparinized (green op) vacutainers and will be transported to the laboratory.

Peripheral blood for plasma inhibitory assay will be drawn pre and post administration of first crenolanib dose on day1 cycle 1 at the following time points: pre dose and at 30 (\pm 10), 60 (\pm 15), 120 (\pm 15) minutes, 4 (\pm 1) hours, 8 (\pm 2), and 24 (\pm 6) hours (Day 2) after crenolanib administration.

In order to obtain the 24-hour time point, all other day 1 dosing (2 doses) will be held. It is also crucial that the 24-hour time point be obtained prior to dose administration on day 2.

Blood samples will also be drawn for plasma inhibitory analysis pre and post administration of first crenolanib dose on day 15 of cycle 1 at the following time points: pre dose, 30 (\pm 10) minutes, and 4 (\pm 1) hours after administration of first crenolanib dose.

Do not administer second or third dose of crenolanib until after 4 hour timepoint is obtained on day 15 of cycle 1.

On subsequent courses, samples may be obtained at the discretion of the investigator (e.g., predose), and whenever possible every 2-4 cycles. (Appendix V).

Sampling Collection and Processing Instructions for Plasma Inhibitory Assay Analysis

Please refer to the lab manual provided by AROG Pharmaceuticals. The date and time of sample collection, crenolanib dose, and date and time of the last crenolanib dose should be recorded on the appropriate Plasma Inhibitory Assay Data Collection Form (Appendix IX-B, X-B and XI-B)

Sampling Handling and Shipping Instructions

Protocol: ARO-005

The participating institution will arrange for shipments of samples collected for plasma inhibitory assay for each patient enrolled on the study.

Samples should be shipped within 30 days of the last sample collection. Specimens collected should be shipped via FedEx Priority Overnight shipping for delivery Monday through Thursday. Weekend and holiday deliveries should be avoided. In preparation of sample shipment, contact AROG Pharmaceuticals (refer to appendix XV) and [name] lab (Appendix XIII) to notify of sample shipment and to provide the FedEx tracking number. AROG Pharmaceuticals will confirm shipment from the site. Ship all plasma inhibitors assay samples on dry ice, along with a completed Data Collection Form (Appendix IX-B, X-B and XI-B)

12.2 Pharmacokinetic Assay

Description of the Assay

Samples collected during study of crenolanib therapy will be collected into no additives added (red top) vacutainers and will be transported to the laboratory.

Sampling Strategy

Peripheral blood for pharmacokinetic studies will be drawn pre and post administration of first crenolanib dose Day 1 of cycle 1 at the following time points:

pre dose and at 30 (\pm 10), 60 (\pm 15), 120 (\pm 15) minutes, 4 (\pm 1) hours, 8 (\pm 2) hours, and 24 (\pm 6) (Day 2) hours after crenolanib administration.

In order to obtain the 24-hour time point, all other day 1 dosing (2 doses) will be held. It is also crucial that the 24-hour time point be obtained prior to dose administration on day 2.

Blood samples will also be drawn for pharmacokinetic analysis pre and post administration of first crenolanib dose on day 15 of cycle 1 at the following time points: pre dose, 30 (\pm 10) minutes, and 4 (\pm 1) hours after administration of the first crenolanib dose.

Do not administer second or third dose of crenolanib until after 4 hour timepoint is obtained on day 15 of cycle 1.

Blood samples will also be drawn for pharmacokinetic analysis pre and post administration of first crenolanib dose on **day 1 of cycle 2** and **day 1 of cycle 3** at the following time points:

- Pre dose
- 4 ± 1 hour

Protocol: ARO-005

Do not administer second or third dose of crenolanib until after 4 hour timepoint is obtained on day 1 of cycle 2 and day 1 of cycle 3.

Peripheral blood sampling for pharmacokinetic assay and bone marrow aspiration for day 1 of cycle 2 should be done on the same day

On subsequent courses, samples may be obtained at the discretion of the investigator (e.g., predose), and whenever possible every 2-4 cycles. (Appendix V).

Sampling Collection and Processing Instructions

Please refer to the lab manual provided by AROG Pharmaceuticals. The date and time of sample collection, crenolanib dose, and date and time of the last crenolanib dose should be recorded on the appropriate Pharmacokinetics Data Collection Form (Appendix IX-A, X-A and XI-A).

Sampling Handling and Shipping Instructions

In preparation of shipping samples, contact AROG Pharmaceuticals (refer to appendix XV) and MicroConstants (Appendix XIII) to notify of sample shipment and to provide FedEx tracking number. AROG Pharmaceuticals will confirmation shipment from site.

Samples should be shipped within 60 days of the last sample collection, whenever feasible. Specimens collected should be shipped via FedEx Priority Overnight shipping for delivery Tuesday through Thursday. Weekend and holiday deliveries should be avoided. Ship all pharmacokinetic samples on dry ice, along with a completed Pharmacokinetics Data Collection Form (Appendix IX-A, X-A and XI-A).

12.3 **Bone Marrow Samples and Other Correlative Studies**

Sampling collection schedule:

Prior to start of first dose of crenolanib, a baseline sample of bone marrow or peripheral blood containing blasts should be obtained. If entry bone marrow aspiration was done per eligibility criteria (within 30 days prior to study drug initiation) as part of screening but no aspirate is available at time of enrollment, obtain 1 green top tube of blood and process per bone marrow aspirate instructions in AROG Pharmaceuticals laboratory manual.

It is preferable that bone marrow aspiration for screening baseline evaluation be done within 14 days of start of study drug and a sample of this marrow should also be shipped as per instructions below.

Additional bone marrow aspirations (x2) should be taken at the following time points:

- Cycle 2 day 1 +4 days*
- Cycle 3 day 1 ± 7 days
- Then every 3 cycles ± 1 cycle as long as criteria for CR is maintained.

Sampling Collection:

Protocol: ARO-005

Bone marrow aspiration (BMA) will be done as per institutional protocol. Please refer to lab manual provided by AROG Pharmaceuticals for additional information.

Refrigerated BMA samples should be shipped within 24 hours of collection along with Data Collection Form.

Shipping of bone marrow samples:

In preparation of marrow sample shipment, contact AROG Pharmaceuticals (refer to appendix XV) and ProPath (Appendix XIII) to notify of sample shipment and provide the FedEX tracking number. AROG Pharmaceuticals will provide confirmation regarding shipment from site. Ship all bone marrow samples on dry ice, along with a completed Data Collection Form (Appendix XII).

^{*}bone marrow sampling day 1 cycle 2 should match sampling days for plasma inhibitory assay and pharmacokinetic assay.

At loss of CR, bone marrow biopsy should be performed as clinically indicated to exclude toxicity issues such as persistent pancytopenia due to study drug vs progressive AML. For patients remaining on study drug without significant toxicity for more than 12 months, subsequent evaluations during study may be modified after discussion with the sponsor.

Blood samples will also be drawn for future correlative science research studies at the following two time point's:

- Pre administration of first dose of crenolanib on day 1 of cycle 1
- Day (+14days) at which patient is determined to have progressive disease by the PI

In preparation of sample shipment, contact AROG Pharmaceuticals (refer to appendix XV) and ProPath (Appendix XIII) to notify of sample shipment and provide the FedEX tracking number. See lab manual/instructions for more details.

Tissue cells and blood samples may be requested for immediate assessment in other tests which assess study drug activity on the biologic targets or samples will be banked for future correlative science research studies. Additional correlative science research may be performed at the discretion of the investigators or AROG, including assays for resistance studies for cases in which responses are noted but are not durable. The total blood drawn for these studies will be less than 400ml in any month.

13. PATIENT EVALUATION

13.1 Pre-Treatment Evaluation

All pretreatment studies should be obtained within 14 days of entry into the trial, unless otherwise stated.

- 1. Medical history (includes documentation of current medications and allergies)
- 2. Height, weight, vital signs
- 3. Physical examination with baseline laboratory tests
- 4. ECOG Performance Status (Appendix III)
- 5. Serum or urine pregnancy test for women of child bearing capacity
- 6. A complete history and physical, documentation of all disease, concomitant medications and performance status
- 7. CBC, platelet count, differential (differential may be omitted if WBC is $<0.5 \times 10^9/L$)
- 8. Creatinine, total bilirubin, ALT, and AST
- 9. HIV infection or hepatitis B or C screening. (positive defined as hepatitis B surface antigen positive or hepatitis C antibody positive)
- 10. Bone marrow aspirate during the last 30 days preceding study initiation is acceptable for study entry as long as blast count is available from that marrow. Cytogenetics will be obtained prior to therapy (results from prior analysis can be used for this purpose, if done within 6-months of enrollment)
- 11. Evaluation of FLT3 mutation status (if not done < 30 days of start of study drug).
- 12. Peripheral blood for optional procedures
- * Every effort will be made to collect optional procedures at all time points for all patients; however, missing collection in one or more of these time points in occasional patients will not be considered a protocol deviation/violation.

13.2 Evaluation during Treatment

- 1. Physical exam at the start of each cycle (\pm 4 days) for the first 2 cycles, then every 2 cycles and documentation of all concomitant medications.
- 2. CBC, platelet count, differential (differential may be omitted if WBC is $<0.5 \times 10^9/L$) twice weekly (at least 24 hours apart) for the first two weeks of cycle 1, once weekly (\pm 3 days) for the second two weeks of cycle 1, bi-weekly (\pm 4 days) for the second cycle and once a month thereof from cycle 3 until cycle 12 (\pm 14 days).
- 3. Creatinine, total bilirubin, ALT, AST, twice weekly (at least 24 hours apart) for the first two weeks of cycle 1, once weekly (±3 days) for the second two weeks of cycle 1, bi-weekly (± 4 days) for the second cycle and once a month thereof from cycle 3 until cycle 12 (± 14 days).
- 4. Bone marrow aspiration x 2 should be taken at these timepoints: cycle 2 day 1 (+4 days), then cycle 3 day 1 (+/- 7 days), then every 3 cycles (+/- 1 cycle) as long as criteria for CR is maintained. At loss of CR, bone-marrow aspiration would be performed only as clinically indicated to exclude toxicity issues like persistent pancytopenia due to study drug vs from progressive AML.

- 5. Peripheral blood for correlative studies will be drawn on day1 at the following time points: pre dose and at 30 (\pm 10), 60 (\pm 15), 120 (\pm 15) minutes, 4 (\pm 1) hours, 8 (\pm 2), and 24 (\pm 6) hours after crenolanib administration. Blood samples will also be drawn on day 15 of cycle 1 at the following time points: pre dose, 30 (\pm 10) minutes, and 4 (\pm 1) hours after crenolanib administration. Blood samples will also be drawn on day 1 cycle 2 (±2 days), day 1 cycle 3 (± 2 days) at the following time points: pre dose, 4 ± 1 hours after crenolanib administration. On subsequent courses, samples may be obtained at the discretion of the investigator, predose, and whenever possible every 2-4 cycles.
- 6. For patients that remain on study with no significant toxicity for more than 12 months, subsequent evaluations during study may be modified after discussion with the sponsor. These may include a decrease in frequency of bone marrow aspirations to every 6-12 months (or as clinically indicated), correlative studies to every 6-12 months (or suspension of sample collection for correlative studies), and other laboratory tests to once every cycle.
- * Every effort will be made to collect optional procedures at all time points for all patients; however, missing collection in one or more of these time points in occasional patients will not be considered a protocol deviation/violation.

Labs obtained with the local physician can be used for monitoring; PI must review and sign source documents within 24 hours of performance of lab at local physician's office unless performed on a Friday in which case review on the following Monday is acceptable. It is encouraged that labs be performed on Monday thru Thursday.

14. CRITERIA FOR RESPONSE

Response criteria will be modified from the International Working Group for AML.²⁷ Responders are patients who obtain a CR, CRi, or PR, with or without cytogenetic response, hematologic improvements, and morphologic leukemia-free state. Briefly, criteria are as follows:

14.1 Complete Remission (CR):

• Peripheral blood counts:

No circulating blasts Neutrophil count $\geq 1.0 \text{ x} 10^9/\text{L}$ Platelet count $\geq 100 \text{ x} 10^9/\text{L}$

• Bone marrow aspirate and biopsy:

≤5% blasts No Auer rods No extramedullary leukemia

14.2 Complete Remission with Incomplete Blood Count Recovery (CRi):

• Peripheral blood counts:

No circulating blasts Neutrophil count $<1.0 \text{ x} 10^9/\text{L}$, or Platelet count $<100 \text{ x} 10^9/\text{L}$

• Bone marrow aspirate and biopsy:

≤ 5% blasts No Auer rods No extramedullary leukemia

14.3 Partial Remission (PR):

• All CR criteria if abnormal before treatment except: ≥50 % reduction in bone marrow blast but still >5% or Marrow blasts <5% with persistent Auer rods

14.4 Morphologic Leukemia-Free State:

• Bone marrow: ≤5% myeloblasts

14.5 Hematologic Improvement (HI):

Hematologic response must be described by the number of positively affected cell lines.

- Erythroid response (E) (pretreatment Hgb <11 g/dL) Hgb increase by ≥1.5 g/dL
- Platelet response (P) (pretreatment platelets $<100 \times 10^9/L$)
 Absolute increase of $\ge 30 \times 10^9/L$ for patients starting with $> 20 \times 10^9/L$ platelets
 Increase from $< 20 \times 10^9/L$ to $> 20 \times 10^9/L$ and by at least 100%
- Neutrophil response (N) (pretreatment ANC $<1.0 \times 10^9$ /L) At least 100% increase and an absolute increase $> 0.5 \times 10^9$ /L
- Blast response (B)

Protocol: ARO-005

At least a 50% reduction in blast percentage in peripheral blood (if > 5%) or bone marrow

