8.2 Exclusion Criteria

- 1. Absence of a FLT3 activating mutation
- 2. <5% blasts in blood or marrow at screening
- 3. Concurrent chemotherapy, or targeted anti-cancer agents, other than hydroxyurea.
- 4. Patient with concurrent severe and/or uncontrolled medical conditions that in the opinion of the investigator may impair the participation in the study or the evaluation of safety and/or efficacy.
- 5. HIV infection or active hepatitis B or C (defined as positive hepatitis B surface antigen positive or hepatitis C antibody positive)
- 6. Known clinically active central nervous system (CNS) leukemia
- 7. Patients who are <30 days of a HSCT.
- 8. Subjects who have clinically significant graft-versus-host disease requiring treatment, and/or have >Grade 2 persistent non hematological toxicity related to the transplant
- 9. Prior crenolanib treatment for non-leukemic indication
- 10. Major surgical procedures within 14 days of Day 1 administration of crenolanib.
- 11. Unwillingness or inability to comply with protocol.

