9.5 Concomitant Medications

Protocol: ARO-005

In general, the use of any concomitant medication/therapies deemed necessary for patient supportive care and safety are permitted. Other anticancer agents including systemic chemotherapy, radiation therapy, or biologic response modifiers are not permitted during the study, with the exception of hydroxyurea which is allowed for 14 days anytime during the first 28 days on study.

Prophylactic intrathecal therapy is allowed to prevent recurrence of CNS disease. Patients with active CNS disease are excluded.

No other investigational drugs are allowed during the study without consent of the medical monitor.

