Appendix II. Inclusion/Exclusion Criteria Checklist

All subjects enrolled must meet eligibility criteria based on the inclusion/exclusion criteria detailed in the application and approved by the IRB. Alternatively MD Anderson internal form can be used.

1. 2	tudy information								
Pro	otocol Title:	A Phase II Study of Crenolanib in Acute Myeloid Leukemia Patients with FLT3 Activating Mutations							
Pro	otocol Number:	ARO-005							
II. S	Subject Informatio	on:							
	bject Name/ID:								
Ge	ender: Male	Female							
Cr	. Inclusion/Exclusiviteria Tom IRB approved p	ion Criteria:Inclusion	Yes	No	N/A	Supporting Documentation*			
1.	radiation therapy, of MPN as defined by presence of FLT3 activating mutation recurred after prior never received a FA) or whose leuke after prior therapy								
2.		ndary AML who have n two prior cytotoxic taining regimens.							
3.	2	eriteria, without any ML, regardless of the							

4.	Patients with primary AML with no more than two prior cytotoxic drug containing salvage regimens. Reinduction with the same agents is not considered a salvage regimen. Change of drugs will be considered a salvage regimen. Unlimited FLT3 TKI therapy (even in combination with cytotoxics/hypomethylating agents) is allowed for patients enrolled in cohort B.		
5.	Positive for AML with FLT3-ITD and/or other FLT3 activating mutations as tested within 30 days of enrollment.		
6.	Age ≥18 years		
7.	ECOG Performance Status 0 - 2		
8.	Liver function: $ALT \le 3.0x \ ULN$ $AST \le 3.0x \ ULN$ Bilirubin $\le 1.5x \ ULN$		
9.	Serum creatinine ≤ 1.5x ULN		
10.	Recovery from toxicities of prior therapy (including HSCT) to no more than grade 1 (except alopecia)		
11.	Subjects should have received no anti- leukemic therapy (except hydroxyurea) for 14 daysfor classical cytotoxic agents and for five times the half life of FLT3 inhibitorsprior to first dose of crenolanib and antineoplastic agents that are neither cytotoxic nor FLT 3 inhibitors.		
12.	Negative pregnancy test for women of childbearing potential		
13.	Able and willing to provide written informed consent		

	clusion Criteria rom IRB approved protocol)	Yes	No	N/A	Supporting Documentation*
1.	Absence of FLT3 activating mutation				
2.	<5% blasts in blood or marrow at screening (i.e. only extra-medullary leukemia)				
3.	Concurrent chemotherapyor targeted anti- cancer agents, other than hydroxyurea.				

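### Exactly 5% marrow blasts counts both as disease at entry and as remission at assessment, so an eligible patient can meet the marrow part of CR/CRi before the first dose

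*Combined protocol and SAP*

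**What the plan says.** **Entry.** Exclusion 2 in Section 8.2, repeated in the synopsis, removes patients with "<5% blasts in blood or marrow at screening". A value of exactly 5% is not excluded. The Appendix II checklist words the same item as "<5% blasts in blood or marrow at screening (i.e. only extra-medullary leukemia", which points to patients with no appreciable disease in either compartment.

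**Response.** CR (14.1) and CRi (14.2) set the same marrow criterion: "≤5% blasts No Auer rods No extramedullary leukemia". Both also require "No circulating blasts". CRi is the category for neutrophils below 1.0 or platelets below 100 (×10⁹/L), with no lower limit on either. Morphologic leukemia-free state (14.4) also uses ≤5%. PR (14.3) requires the CR criteria where abnormal before treatment, except for "≥50 % reduction in bone marrow blast but still >5% or Marrow blasts <5% with persistent Auer rods".

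**Endpoint.** "Responders are patients who obtain a CR, CRi, or PR" (Section 14). Section 16.1 compares the number of responders with fixed bars: 2 of 28 and then 5 of 40 in Cohort B, and 2 of 24 and then 4 of 30 in Cohort A.

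**The concern.** Cut-offs for disease and for remission should meet without sharing a value. Here they share 5%. PR requires a relative fall in blasts and hematologic improvement (14.5) sets pretreatment thresholds, but CR and CRi refer to no baseline value. Nothing in the documents says how to score a patient whose baseline marrow already satisfies the limit.

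The bars are low, so single patients matter. One responder is 1/5 = 20% of the final bar in Cohort B and 1/4 = 25% in Cohort A, and half of the stage 1 bar in each. A patient counted without any change in the marrow weakens the futility stop and raises the chance that an inactive drug is called active.

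**Working it through.** **1. Which patients are affected, under each reading of exclusion 2**

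| Patient at screening | Literal reading (excluded if either site is <5%) | Appendix II reading (excluded only if both sites are <5%) |
|---|---|---|
| Marrow exactly 5%, no blood blasts, no Auer rods, no extramedullary disease, low counts | Not eligible | Eligible, and meets every CRi criterion |
| Marrow exactly 5%, blood ≥5% | Eligible; marrow blast limit met, blood must clear | Same |
| Marrow <5%, blood ≥5% | Not eligible | Eligible; marrow blast limit met, blood must clear |

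The overlap at exactly 5% exists under both readings. Only the Appendix II reading admits a patient who meets full CRi before treatment, or one with marrow blasts below 5%.

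**2. A gap at the same value.** Exactly 5% marrow blasts with Auer rods is not CR or CRi, which allow no Auer rods. It is not PR either, since PR needs more than 5%, or "Marrow blasts <5% with persistent Auer rods". This gap loses responders; it does not add any.

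**3. The plan's own figures (Section 16.1).** With stage 1 size n₁ and response rate p, stopping at 1 or fewer responders has probability (1−p)^n₁ + n₁·p·(1−p)^(n₁−1). At p = 0.05:

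- Cohort B, n₁ = 28: 0.238 + 0.350 = 0.588 (plan: 59%).
- Cohort A, n₁ = 24: 0.292 + 0.369 = 0.661 (plan: 66%).

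The probability of a false 'active' verdict is the sum, over x ≥ 2 stage 1 responders, of P(x) times the probability that stage 2 brings the total to the final bar (5 of 40, or 4 of 30). This gives 0.0472 in B (plan alpha 0.05) and 0.0599 in A (plan alpha 0.06). The corresponding betas are 0.079 at a 20% response rate and 0.0098 at 30% (plan: 0.08 and 0.01). The designs reproduce.

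**4. Upper-bound sensitivity.** Let q be the share of patients who meet the cut-off at baseline. The documents do not give q, so the range is an assumption. Score all of these patients as responders and let the rest respond at 5%. The counted rate under the null is then p = 0.05 + 0.95q, put through the same two-stage calculation.

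| q | p | Expected such patients, B (40q) / A (30q) | False 'active', B | False 'active', A |
|---|---|---|---|---|
| 0 | 0.0500 | 0 / 0 | 0.047 | 0.060 |
| 0.25% | 0.0524 | 0.1 / 0.075 | 0.056 | 0.069 |
| 0.5% | 0.0548 | 0.2 / 0.15 | 0.065 | 0.078 |
| 1% | 0.0595 | 0.4 / 0.3 | 0.086 | 0.099 |
| 2.5% | 0.0738 | 1.0 / 0.75 | 0.167 | 0.175 |
| 5% | 0.0975 | 2.0 / 1.5 | 0.346 | 0.332 |

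**5. One automatic responder in stage 1.** The trial then stops early only if none of the other n₁ − 1 patients responds. In B this is 0.95^27 = 0.250 instead of 0.588; in A it is 0.95^23 = 0.307 instead of 0.661. The false 'active' probability becomes 0.129 in B and 0.174 in A. These figures need no assumed share, but they are conditional on one such patient being enrolled in stage 1 and scored a responder.

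**The case against.** **Meeting the marrow criterion is not being a responder.** CR and CRi also need no circulating blasts, no Auer rods and no extramedullary leukemia. Response is judged after cycle 1 and at best response (Section 1.1), with marrows at cycle 2 day 1 and cycle 3 day 1 (Section 13.2), not at screening. A patient with relapsed or refractory disease must still be at or below 5% about 28 days later. This stands, and it is why the table is an upper bound.

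**A reader might infer that any eligible patient with 5% marrow blasts is already a full CRi.** The documents do not support that. It needs the Appendix II reading and all the other CRi conditions. Under the literal wording no eligible patient meets full CRi at baseline.

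**A reader might also infer that hydroxyurea turns such patients into false responders**, because Section 9.5 permits "hydroxyurea which is allowed for 14 days anytime during the first 28 days on study". It could contribute to clearing blood blasts. But the allowance applies to every patient, clearance may equally reflect crenolanib, and the documents do not separate the two. It is a different question from the cut-offs.

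**The overlap is narrow.** Under the literal reading it is a single value, and nothing in the documents shows that any patient sits there. At a share of 0.25% the change is below 0.01 in both cohorts. This stands as an argument about severity. It does not remove the contradiction.

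**Conclusion.** The cut-offs overlap at exactly 5% marrow blasts on the face of the text, and no other section resolves this. Under the Appendix II wording the overlap extends to a patient who meets full CRi at screening and to patients with marrow blasts below 5% and blood blasts of at least 5%. Under the literal wording only the marrow overlap at 5% remains.

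The effect could be negligible or material. On the upper-bound assumption it runs from 0.056 to 0.346 in Cohort B and from 0.069 to 0.332 in Cohort A for shares of 0.25% to 5%. It would be wrong to read 0.346 as the trial's actual false-positive rate: it requires 5% of enrolled patients to be in the overlap and every one to be scored a responder, and the documents give no figure for either. Nor is the sample size calculation at fault, since it reproduces.

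This is a should-fix clarification of the primary endpoint. The documents do not demonstrate a must-fix error.

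**What to change.** 1. In 14.1, 14.2 and 14.4, replace ≤5% with <5%. In the PR reduction rule in 14.3, replace >5% with ≥5%. The cut-offs then meet with neither overlap nor gap.
2. Reconcile exclusion 2 across the synopsis, Section 8.2 and Appendix II, so that it is clear whether one compartment or both must be below 5% for exclusion. Step 1 alone does not deal with patients who enter with marrow blasts below 5%.
3. In Section 16.3, add a sensitivity analysis of the response rate that counts patients whose baseline marrow was already <5% as non-responders. This is preferable to barring them from response in the primary analysis. Keeping them in the denominator with no chance of responding would bias the rate downward, and some may have cleared blood blasts through a real drug effect.

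**Cost.** The change is wording plus one extra analysis; Section 13.1 already requires a blast count from the entry marrow. The downside is that a patient at exactly 5% after treatment is no longer CR or CRi. If counts were low before treatment and remain so, that patient is not PR either, because PR keeps the CR count thresholds, and so becomes a non-responder. The reported response rate may be slightly lower.

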16. STATISTICAL CONSIDERATIONS

16.1 Determination of Sample Size

The primary endpoint of the study is the overall response rate to crenolanib. The outcome may be different for patients with or without the previous FLT3 TKI therapy. Therefore, patients will be stratified according to whether they have recurred after prior chemotherapy without a FLT3 TKI treatment or they have progressed after prior therapy with a FLT3 TKIs.

Based on the promising results observed to date, the sample size for each cohort will be expanded to include a total of 30 patients in Cohort A and 40 patients in Cohort B. Such additional patients will permit a more accurate assessment of the efficacy and safety of crenolanib in these populations. The total sample size for the two cohorts is 70 patients.

Cohort B (N=40): Two parallel Simon minimax two-stage Phase II designs will be used for the two cohorts of patients. For the patients who progressed after prior chemotherapy with FLT3 TKI, the null response rate will be 5%, and target response rate will be 20%. With alpha of 0.05 and beta of 0.08, the first stage will require 28 patients. If there is 1 or no patient responding, the trial will be stopped. If 2 or more out of the first 28 patients respond, accrual will continue until a total of 40 patients have been enrolled. At the end of the study, if 5 or more patients out of 40 respond, the regimen will be considered active. With this design, the probability of early termination is 59% if the true response rate is only 5%.

Cohort A (N=30): For the patients who progressed after prior chemotherapy without FLT3 TKI, the null response rate will be 5%, and target response rate will be 30. With alpha of 0.06 and beta of 0.01, the first stage will require 24 patients. If there is 1 or no patient experiencing the response, the trial will be stopped. If 2 or more out of the first 24 patients respond, accrual will continue until a total of 30 patients have been enrolled. At the end of the study, if 4 or more patients out of 30 respond, the regimen will be considered active. With this design, the probability of early termination is 66% if the true response rate is only 5%.

The method of Thall, Simon, and Estey will be employed to perform interim safety monitoring. We will assume a Beta (0.6, 1.4) prior distribution for the toxicity rate which in particular has mean of 30%. The toxicity is defined as any grade 3 or greater non-hematologic toxicities attributed to the study drug.

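### As worded, PR waives the CR blood and extramedullary items that were normal at entry, so new circulating blasts or newly fallen counts need not stop a patient counting as a responder

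*Combined protocol and SAP*

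**What the plan says.** - Section 16.1: "The primary endpoint of the study is the overall response rate to crenolanib".
- Section 14: "Responders are patients who obtain a CR, CRi, or PR". Section 1.1 names the same three categories in the primary objective.
- Sections 14.1 and 14.2: CR and CRi each require absence of circulating blasts and of extramedullary leukemia, with no reference to the baseline value. CR also requires neutrophils of at least 1.0 x10⁹/L and platelets of at least 100 x10⁹/L. CRi accepts a shortfall in either count, provided marrow blasts are at most 5%.
- Section 14.3: PR is "All CR criteria if abnormal before treatment except: ≥50 % reduction in bone marrow blast but still >5" percent, or "Marrow blasts <5% with persistent Auer rods".
- Section 14 introduces the whole list with "Response criteria will be modified from the International Working Group for AML" and says that it is given in brief.
- Section 16.1: two two-stage designs with a 5% null rate. In Cohort A, "if 4 or more patients out of 30 respond, the regimen will be considered active"; in Cohort B the mark is 5 of 40. Both continue past stage 1 on 2 responders.

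**The concern.** The baseline condition in 14.3 makes sense as a statement that abnormal items must recover. It does not say that normal items must stay normal. The result is uneven: baseline platelets of 90 x10⁹/L must reach 100 for PR, while baseline platelets of 110 may fall without limit. A patient with no blasts in the blood at entry may have them at the response assessment.

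Waiving a criterion can only add responders, so any error runs upward. It would enter the primary response rate, its confidence interval and the two-stage counts, where the pass marks are only 4 and 5 patients.

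**Working it through.** **Which items bind.** For each item, under the wording of 14.1 to 14.3:

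| Item at response | CR | CRi | PR, item abnormal at baseline | PR, item normal at baseline |
|---|---|---|---|---|
| No circulating blasts | required | required | required | not stated |
| No extramedullary leukemia | required | required | required | not stated |
| ANC ≥1.0 x10⁹/L | required | may be lower | required | not stated |
| Platelets ≥100 x10⁹/L | required | may be lower | required | not stated |

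The gap is the last column. A patient reaches it only by also meeting a marrow route for PR and having every baseline-abnormal item normalised.

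**Does another section close it?** Sections 7 and 9.4 make progression a reason to stop treatment, and section 12.3 leaves its determination to the investigator. No section defines progression or says that it cancels a PR.

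**Can such patients enrol?** No eligibility criterion requires low counts or extramedullary disease. For circulating blasts, the checklist in Appendix II explains exclusion 2 as "<5% blasts in blood or marrow at screening (i.e. only extra-medullary leukemia", which admits marrow disease without circulating blasts. Section 14.5 points the same way: its blast-response rule applies to peripheral blood only above 5%, which anticipates patients below that level.

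**The plan's own figures.** Inputs from section 16.1:
- Cohort A: n1 = 24, n = 30, pass mark r = 4
- Cohort B: n1 = 28, n = 40, pass mark r = 5
- Both: continue if at least 2 respond; null rate 0.05

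P(active | p) = Σ over x from 2 to n1 of P[Bin(n1, p) = x] × P[Bin(n − n1, p) ≥ r − x]

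Cohort A at p = 0.05:
- Early stop: 0.2920 + 0.3688 = 0.661 (stated 66%).
- Active: 0.2232 × 0.0328 + 0.0862 × 0.2649 + 0.0298 = 0.060 (stated 0.06). The last term is P(4 or more in stage 1).

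Cohort B at p = 0.05:
- Early stop: 0.2378 + 0.3505 = 0.588 (stated 59%).
- Active: 0.2490 × 0.0196 + 0.1136 × 0.1184 + 0.0374 × 0.4596 + 0.0117 = 0.047 (stated 0.05). The last term is P(5 or more in stage 1).

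The same formula at the target rates gives beta of 0.010 in A (stated 0.01) and 0.079 in B (stated 0.08). The stated design reproduces.

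**Illustration of sensitivity.** The documents give no rate for the PRs at issue. Assume that they add δ to a true rate of 5%, and put p = 0.05 + δ in the formula:

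| δ (points) | Expected extra PRs, A (30δ) | P(active), A | Expected extra PRs, B (40δ) | P(active), B |
|---|---|---|---|---|
| 0 | 0 | 0.060 | 0 | 0.047 |
| 0.25 | 0.075 | 0.069 | 0.10 | 0.056 |
| 0.5 | 0.15 | 0.079 | 0.20 | 0.066 |
| 1 | 0.30 | 0.101 | 0.40 | 0.088 |
| 3 | 0.90 | 0.213 | 1.20 | 0.210 |

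Expected extra PRs are for a cohort that runs to full size. The 3-point row means about one such patient per cohort, a 60% increase on the null rate (3/5). It is an upper illustration, not an estimate.

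**The case against.** The case for treating this as a minor clarification has real weight.

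- **The joint event is narrow.** A reader might infer that any patient whose marrow blasts halve while blasts appear in the blood is scored PR. The text does not support that: every item abnormal at baseline must still have normalised. Section 10.3 says that leukemia patients usually present with abnormal blood counts, so few will have normal items to lose. This stands.
- **The new-blasts case depends on a reading.** Section 8.2 and the synopsis exclude patients with under 5% blasts in blood or marrow. If that excludes a shortfall at either site, everyone has circulating blasts at entry and this case is empty. The checklist explanation and section 14.5 favour the other reading, but the body text is ambiguous. New extramedullary disease and falling counts do not depend on it.
- **Cytopenia alone is the weaker half.** CRi already accepts low counts without a floor, so low counts do not in themselves bar response here. CRi does, however, require marrow blasts of at most 5% and no Auer rods, whereas the PR routes allow more than 5% or persistent Auer rods.
- **The brief list may assume that normal items stay normal.** The synopsis names the International Working Group criteria. That may be the intent, but the criteria are expressly modified and the requirement is not printed.
- **The null may already include such PRs.** The 5% null is a rate for an endpoint that contains PR. Adding points on top supposes that it was set under a stricter PR definition, which no section says. This is why the table is only an illustration.

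**Conclusion.** The gap in wording is real and bears on the primary endpoint. Section 14.3 read literally can count as a responder a patient with new circulating blasts, new extramedullary leukemia or newly fallen counts, provided that a marrow route is met and every baseline-abnormal item has normalised. Nothing else in the protocol overrides that classification. Any bias is upward.

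Its size is unknown. The affected group is probably small, and the illustrative range (0.069 to 0.213 in Cohort A, 0.056 to 0.210 in Cohort B, against 0.060 and 0.047) rests entirely on assumed increments of 0.25 to 3 points. A reader might infer from the upper end that the trial's type I error is about 0.21, or that the Simon calculations are faulty. Neither follows: the stated error rates and stopping probabilities reproduce, and the documents do not show that even one such PR has occurred. The reason to act is that the pass marks are low enough for a single misclassified patient to matter, and that the repair is simple.

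**What to change.** In section 14.3, delete the condition that stands between the words criteria and except, and list the items so that nothing is left to inference. At the response assessment, whatever the baseline value, PR requires:

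- no circulating blasts;
- ANC ≥1.0 x10⁹/L;
- platelets ≥100 x10⁹/L;
- no extramedullary leukemia;
- and either existing marrow route: a reduction in marrow blasts of at least 50% but still above 5%, or marrow blasts below 5% with persistent Auer rods.

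Both marrow routes should be named, so that the edit does not drop the Auer-rod route. Items abnormal at baseline must already meet these thresholds, so the change affects only items that were normal at entry. Re-read recorded PRs against the new wording before the analysis. If the sponsor does intend the exception, the protocol should say so and such PRs should be reported separately.

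Cost: a wording amendment and a re-read of recorded PRs. The reported PR rate may be slightly lower. No new assessments are needed, because section 13.2 already schedules blood counts in every cycle and physical examinations through treatment. It allows the differential to be omitted when WBC is below 0.5 x10⁹/L, but neutrophils cannot exceed WBC, so such a patient fails the ANC item in any case.
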